8.7.2. Retained Research Samples for Biomarkers

These Retained Research Samples will be collected in this study:

• A 2 mL whole blood Prep B2.5 optimized for serum as outlined in the SoA.

Retained Research Samples will be collected as local regulations and IRB/ECs allow according to the SoA.

Retained Research Samples may be used for research related to the study intervention(s). Genes and other analytes (eg, proteins, RNA, nondrug metabolites) may be studied using the retained samples.

See Appendix 5 for information regarding genetic research. Details on processes for collection and shipment of these samples can be found in in the lab manual and other supporting documentation.

8.8. Immunogenicity Assessments

Immunogenicity assessments are not included in this study.

8.9. Health Economics

Health economics/medical resource utilization and health economics parameters are not evaluated in this study.

9. STATISTICAL CONSIDERATIONS

Detailed methodology for summary and statistical analyses of the data collected in this study is outlined here and further detailed in the SAP, which will be maintained by the sponsor. The SAP may modify what is outlined in the protocol where appropriate; however, any major modifications of the primary endpoint definitions or their analyses will also be reflected in a protocol amendment.

9.1. Statistical Hypothesis

No formal statistical hypothesis testing will be performed in this study.

9.2. Analysis Sets

For purposes of analysis, the following analysis sets are defined:

Participant Analysis	Description
Set	
Enrolled	"Enrolled" means a participant's, or their legally authorized
	representative's, agreement to participate in a clinical study
	following completion of the informed consent process and
	randomization to study intervention.
Safety analysis set	All participants randomly assigned to study intervention and
	who take at least 1 dose of study intervention. Participants will
	be analyzed according to the product they actually received.

Participant Analysis Set	Description
PK Concentration Set	All participants randomly assigned to study intervention and who receive at least 1 dose of study intervention and in whom at least 1 plasma concentration value is reported.
PK Parameter Set	All participants randomly assigned to study intervention and who receive at least 1 dose of study intervention and have at least 1 of the PK parameters of interest calculated.

9.3. Statistical Analyses

The SAP will be developed and finalized before any analyses are performed and will describe the analyses and procedures for accounting for missing, unused, and spurious data. This section is a summary of the planned statistical analyses of the primary and secondary endpoints.

9.3.1. Safety Analyses

All safety analyses will be performed on the safety population (safety analysis set).

AEs, ECGs, BP, pulse rate, respiratory rate, temperature, continuous cardiac monitoring, and safety laboratory data will be reviewed and summarized on an ongoing basis during the study to evaluate the safety of participants. Any clinical laboratory, ECG, BP, pulse rate, respiratory rate and temperature abnormalities of potential clinical concern will be described. Safety data will be presented in tabular and/or graphical format and summarized descriptively, where appropriate.

Medical history and physical examination and neurological examination information, as applicable, collected during the course of the study, will be considered source data and will not be required to be reported, unless otherwise noted. However, any untoward findings identified on physical and/or neurological examinations conducted during the active collection period will be captured as AEs, if those findings meet the definition of an AE.

Data collected at screening that are used for inclusion/exclusion criteria, such as laboratory data, ECGs, and vital signs, will be considered source data, and will not be required to be reported, unless otherwise noted. Demographic data collected at screening will be reported.

9.3.1.1. Electrocardiogram Analyses

Changes from baseline for the ECG parameters HR, QT interval, QTcF, PR interval, and QRS complex will be summarized by treatment and time. The frequency of uncorrected QT values above 500 ms will be tabulated.

The number (%) of participants with maximum post-dose QTcF values and maximum increases from baseline in the following categories will be tabulated by treatment:

Safety QTcF Assessment

egree of Prolongation Mild (ms) Moderate (ms) Severe (ms)	Moderate (ms) Severe (ms)	Mild (ms)	Degree of Prolongation
---	---------------------------	-----------	------------------------

Absolute value	>450-480	>480-500	>500
Increase from baseline		30-60	>60

If more than 1 ECG is collected at a nominal time after dose administration (for example, triplicate ECGs), the mean of the replicate measurements will be used to represent a single observation at that time point. If any of the 3 individual ECG tracings has a QTcF value >500 ms, but the mean of the triplicates is not >500 ms, the data from the participant's individual tracing will be described in a safety section of the CSR in order to place the >500 ms value in appropriate clinical context. However, values from individual tracings within triplicate measurements that are >500 ms will not be included in the categorical analysis unless the average from the triplicate measurements is also >500 ms. Changes from baseline will be defined as the change between the postdose QTcF value and the average of the pre-dose triplicate values at -1, -0.5, and 0 hours pre-dose on Day 1.

In addition, an attempt will be made to explore and characterize the relationship between plasma concentration and QT interval length using a PK/PD modeling approach. If a PK/PD relationship is found, the impact of participant factors (covariates) on the relationship will be examined. The results of such analyses may not be included in the CSR.

9.3.2. PK Analysis

The PK concentration and parameter populations are defined in Section 9.2.

9.3.2.1. Derivation of PF-06954522 PK Parameters

The plasma PK parameters for PF-06954522, following oral dose administration, will be derived from the plasma concentration-time profiles using standard noncompartmental methods as detailed in Table 4, as data permit. Actual PK sampling times will be used in the derivation of PK parameters. If actual PK sampling times are not available, nominal PK sampling times will be used in the derivation of PK parameters.

Table 4. Plasma PF-06954522 PK Parameters

Parameter	Definition	Method of Determination
AUClast	Area under the plasma concentration-time profile from time 0 to the time of the last quantifiable concentration (C _{last})	Linear/Log trapezoidal method
AUCinf*	Area under the plasma concentration-time profile from time 0 extrapolated to infinite time	AUC _{last} + (C _{last} */k _{el}), where C _{last} * is the predicted plasma concentration at the last quantifiable timepoint estimated from the log-linear regression analysis
Cmax	Maximum plasma concentration	Observed directly from data
Tmax	Time for C _{max}	Observed directly from data as time of first occurrence
t _{1/2} *	Terminal elimination half-life	Loge(2)/kel, where kel is the terminal phase rate constant calculated by a linear regression of the log-linear concentration-time curve. Only those

Parameter	Definition	Method of Determination
		data points judged to describe the terminal log-linear decline will be used in the regression.
CL/F *	Apparent clearance	Dose/AUCinf
V _z /F *	Apparent volume of distribution	Dose/(AUCinf·kel)
AUClast(dn)	Dose-normalized AUClast	AUClast/Dose
AUCinf(dn)*	Dose-normalized AUCinf	AUCinf/Dose
C _{max} (dn)	Dose-normalized C _{max}	C _{max} /Dose

Plasma PF-06954522 PK Parameters Table 4.

9.3.2.2. Statistical Methods for PK Data

Plasma concentrations of PF-06954522 will be listed and summarized descriptively by dose (and fasting condition and ethnicity, if appropriate) and nominal PK sampling time. Individual participant and median profiles of the plasma concentration-time data will be plotted by dose (and fasting condition and ethnicity, if appropriate) using actual (for individual) and nominal (for median) times respectively. Median profiles will be presented on both linear and semi-log scales.

The plasma PK parameters will be summarized descriptively by dose (and fasting condition and ethnicity, if appropriate) as applicable. Dose-normalized AUC_{inf}, AUC_{last}, and C_{max} will be plotted against dose (and fasting condition and ethnicity, if appropriate) using box and whisker plots and will include individual participant values and the geometric means for each dose. These plots will be used to understand the relationship between PK parameters and dose (and fasting condition and ethnicity, if appropriate).

If the food effect is assessed, a mixed effects ANOVA will be performed separately on the natural log transformed AUC_{inf}, AUC_{last}, and C_{max} (dose-normalized prior to analysis, if appropriate) with fasting condition included as a fixed effect and participant as a random effect. Further details of this analysis will be provided in the SAP.

Additional PK analyses may be performed if deemed appropriate and may not be included in the CSR.

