4.2. Scientific Rationale for Study Design

As is typical in the case for FIH studies, the population planned for this study will be healthy adult male and female participants of nonchildbearing potential. Female participants will be confirmed not to be of childbearing potential because reproductive toxicity studies with PF-06954522 have not been conducted. In male participants, appropriate measures are expected to be followed to minimize potential transfer of PF-06954522 via semen to partners (see Appendix 4).

The highest anticipated C_{max} and AUC_{24} of PF-06954522 will not exceed the pre-defined human exposure stopping limits. Furthermore, to permit an unbiased assessment of safety, the participants' treatment assignments (active treatment versus placebo) will be blinded to both site staff (except those involved in preparation of doses) as well as the study participants. However, to permit real-time review of the safety, tolerability, and PK data, a limited number of sponsor study team members will be unblinded.

Given the current study is the first time PF-06954522 will be administered to humans, an escalating single, oral dose crossover design is planned with careful assessment and ongoing review of safety, tolerability, and PK data of PF-06954522. The crossover design will permit both a within- and between-participant assessment of safety/tolerability and PK at multiple dose levels and placebo. The optional Cohort 2 may be included if, based on emerging data from the Cohort 1, it is deemed necessary to meet the objectives of this study.

The optional Cohort 3 (Japanese participants) is included in this study to potentially collect safety, tolerability and PK data that may facilitate development of PF-06954522 in Japan. Continuous cardiac monitoring via telemetry will not be performed in this cohort, and the schedule of ECG/vital sign measurements may be less intensive (see SoA), because the doses administered in this cohort would have been investigated and deemed sufficiently safe in a previous cohort.

For a given participant, it is planned that dosing will be separated by at least 7 days. This planned washout interval is deemed sufficient CCI

(see Section 4.3.1). In addition, PK samples are planned to be collected over 72 hours post-dose to ensure sufficient characterization of PK profile and to account for any

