# 3.3. Other Endpoint(s)

# 3.3.1. Additional Plasma PF-06954522 PK Parameters

Additional plasma PF-06954522 PK parameters, as described in Table 3, will be determined:

Table 3. Additional PF-06954522 Plasma PK Parameters

Parameter	Definition	Method of Determination	Analysis Scale	Analysis Method
AUC inf (dn)*	Dose-normalized AUC inf	AUC inf /Dose	ln	D
AUC last (dn)	Dose-normalized AUC last	AUC last /Dose	ln	D
C max (dn)	Dose-normalized C max	C max /Dose	ln	D
CL/F*	Apparent clearance	Dose/AUC inf	ln	D
V z /F*	Apparent volume of distribution	Dose/(AUC inf x k el )	ln	D

\*=if data permits.

Abbreviations: D=displayed with descriptive statistics as outlined in Table 6 in Section 6.3.1; dn = normalized to a 1 mg PF-06954522 dose; ln=natural-log transformed; R = raw (untransformed).

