# **6.2. Secondary Endpoint(s)**

Plasma PK parameters for PF-06954522, as described in Section 3.2, will be listed and summarized descriptively by treatment and day, as applicable, for participants in the PK Parameter Set (as defined in Section 4). Missing values will be handled as detailed in Section 5.3.

Each PK parameter will be summarized by treatment and day (as appropriate) using the summary statistics as specified in the table below:

Table 5. Summary Statistics for PF-06954522 Plasma PK Parameters

Parameter	Summary Statistics
AUC last , AUC inf *, and C max	N, arithmetic mean, median, CV%, standard deviation,
	minimum, maximum, geometric mean and geometric
	CV%.
T max	N, median, minimum, maximum.
t 1/2 .*	N, arithmetic mean, CV%, standard deviation, median,
	minimum, maximum.

\*: if data permit

Supporting data from the estimation of  $AUC_{inf}$  and  $t_{1/2}$  will be listed by dose: terminal phase rate constant ( $k_{el}$ ); goodness of fit statistic from the log-linear regression ( $r^2$ ); the percent of  $AUC_{inf}$  based on extrapolation ( $AUC_{extrap\%}$ ); and the first, last, and number of time points used in the estimation of  $k_{el}$ . This data may be included in the clinical study report.

The following plots will be presented using the PK Parameter Set (as defined in Section 4):

Box and whisker plots for dose-normalized PK parameters [AUCinf (dn), AUClast (dn) and Cmax(dn)] will be presented in logarithmic scale by treatment and overlaid with observed values of individual participants and geometric means. Geometric means will

have a different symbol than the individual values. Individual values from different cohorts will also have a different symbol. A footnote will be added to the plots to indicate that geometric means are presented and that data from all cohorts are presented on the plot.

The following will additionally be presented for the plasma concentration data using the PK Concentration Set (as defined in Section 4):

- a listing of all concentrations sorted by participant ID and nominal time post-dose for each treatment separately. The concentration listing will also include the actual times. Deviations from the nominal time will be given in a separate listing.

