# 6.3.2. Plasma PF-06954522 PK Parameters During Food Effect Period (if conducted)

Plasma PK parameters for PF-06954522 in the fed state as described in Section 3.3.2 will be listed and summarized descriptively as described in Section 6.2 for participants in the PK Parameter Set as defined in Section 4.

A mixed effects ANOVA, as described in Section 5.2.3, will be performed separately on the natural log transformed AUCinf (if data permit), AUClast, and Cmax (all dose-normalized prior to analysis, if appropriate) with dietary allocation included as a fixed effect and participant as a random effect, using only data from the respective periods that includes the two treatments of interest. The test treatment will be PF-06954522 administered with food in comparison to the reference treatment of PF-06954522 administered in the fasted state.

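### How PK depends on dose is to be read from unlinked box plots; a random-participant power model on the same data would add a slope and interval at little cost

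*Protocol*

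**What the plan says.** Protocol 9.3.2.2 describes box plots of dose-normalised AUCinf, AUClast and Cmax against dose, which "will include individual participant values and the geometric means for each dose". It then states their purpose: "These plots will be used to understand the relationship between PK parameters and dose".

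SAP 6.2 carries the display over ("Box and whisker plots for dose-normalized PK parameters", on a log scale) and adds: "Individual values from different cohorts will also have a different symbol". The symbols therefore separate cohorts. Nothing in either text joins or identifies the same participant across doses.

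SAP Table 3 gives the dose-normalised parameters the single analysis code D, defined as "D=displayed with descriptive statistics as outlined in Table 6 in Section 6.3.1". SAP Table 2 also gives AUCinf, AUClast and Cmax the code for a statistical model, where applicable. The only PK model then described is the fed-versus-fasted mixed model (SAP 5.2.3, 6.3.2 and Appendix 1), fitted "using only data from the respective periods that includes the two treatments of interest". Protocol 9.3.2.2 allows further PK analyses but does not specify them, and they may stay out of the study report.

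On the design, Protocol 4.2 says: "The crossover design will permit both a within- and between-participant assessment of safety/tolerability and PK at multiple dose levels and placebo".

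**The concern.** The plan names a question, how exposure depends on dose, and answers it by eye. The reader gets no estimate and no statement of uncertainty. The by-dose boxes do not use the repeated measurements that the design provides. With about 2 of 10 Cohort 1 participants on placebo in each period, each box can also hold a somewhat different set of people.

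The second issue concerns AUClast only. By definition it stops at the last quantifiable concentration. If low doses fall below the assay limit sooner, AUClast(dn) is cut shorter at low doses and rises with dose even when PK is exactly linear. Such a bias always points towards more-than-proportional exposure.

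At stake is the quality of the dose-exposure statement that the study report hands to later studies.

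**Working it through.** **The plan's own figure.** The documents state no precision or proportionality figure. The only number to reproduce is the sample size: (8+2) + (6+2) + (4+2) = 10 + 8 + 6 = 24, which agrees with Protocol 9.5.

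**Inputs from the documents.** Cohort 1 has about 10 participants, 8 on active drug and 2 on placebo per period (Protocol 9.5). There are five periods, the last anticipated to be fed (Protocol 1.2), which leaves four fasted levels. Dose steps are up to about half-log (Protocol 4.3.4). Intervals are 90% (SAP 5.2.3). Sampling runs to 72 h (Protocol 4.2).

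**Assumptions, not in the documents.** Between-participant CV is 40% and within-participant CV 25%, varied from 20% to 40%. Every step is a full half-log. There are five pairs of participants. Four pairs each take placebo in one fasted period and one pair takes none, so active fasted profiles number 8×3 + 2×4 = 32, or 8 per dose.

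**Slope precision.** The model is ln(parameter) = a + b·ln(dose) + participant + error, with log-scale variance ln(1+CV²).

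- Between: ln(1.16) = 0.1484. Within: ln(1.0625) = 0.0606.
- Spread of ln(dose): 8 × (ln √10)² × (1.5² + 0.5² + 0.5² + 1.5²) = 8 × 1.3255 × 5 = 53.02.
- Paired slope (generalised least squares under this covariance): SE 0.0351. Residual degrees of freedom are 32 − 10 − 1 = 21 and t is 1.72, so the 90% half-width is 1.72 × 0.0351 = 0.060.
- Unpaired slope. With 8 values per dose this is the line through the plotted log geometric means. Its true SE under the same correlated data is 0.0429. Ratio: 0.0429/0.0351 = 1.22.
- Ratio at within-CV 40%: 0.0592/0.0546 = 1.08. At within-CV 20%: 0.0379/0.0283 = 1.34.
- Nominal SE if independence is wrongly assumed: √[(0.1484+0.0606)/53.02] = 0.063, or 1.79 times the paired SE. This is the error of a miscalculated interval. It is not the imprecision of the displayed trend.

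Smaller steps cost precision. With 2-fold steps the paired half-width is 0.081, 0.119 and 0.156 at within-CV 20%, 30% and 40%.

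**AUClast truncation under exact proportionality.** Assume one compartment and ka = 1/h. Then AUC(0–u) is proportional to (1−e^(−ku))/k − (1−e^(−ka·u))/ka, with k = ln 2/half-life.

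| Half-life (h) | AUC0–24 (relative) | AUC0–72 (relative) | Ratio |
|---|---|---|---|
| 4 | 4.681 | 4.771 | 1.02 |
| 8 | 9.099 | 10.519 | 1.16 |
| 12 | 11.984 | 16.042 | 1.34 |

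For the 12 h case to have its last quantifiable sample at 24 h and none at 36 h, lowest-dose Cmax must lie between about 3.2 and 6.3 times the assay limit. At the scheduled sampling times, over the same half-lives and 3.3-fold steps, lowest-dose AUClast(dn) relative to the top dose was:

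- 0.48 to 0.71 when lowest-dose Cmax is 3 times the limit;
- 0.85 to 0.88 at 10 times;
- 0.98 to 1.00 at 100 times.

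AUCinf(dn) stayed within 2% where a terminal slope could be fitted. Cmax(dn) was unaffected.

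**Does the model cure truncation?** No. In simulated trials (150 per setting, half-life 8 h, CVs 40%/25%, true slope 1), the mean AUClast slope was 1.097, 1.049 and 1.016 when lowest-dose Cmax was 5, 10 and 30 times the limit. Coverage of the 90% interval was about 28%, 70% and 84%. The Cmax slope averaged 1.00 with about 90% coverage. The added model should therefore not rest on AUClast.

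**The case against.** The strongest reply is that the plan already answers its stated objective. PK is to be characterised, dose proportionality is not a named objective or endpoint, and no hypothesis is tested. Individual values and geometric means are overlaid, and CL/F is summarised by dose. SAP 6.2 also provides concentration-time plots by participant, counts of concentrations above the assay limit at each time, and a listing of the extrapolated share of AUCinf. A careful reader could spot truncation by setting AUClast(dn) beside AUCinf(dn). All of this stands, and it makes the point optional. What remains is that none of these outputs gives a slope or an interval.

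A reader might infer that poor plots would mislead dose escalation. The documents do not support that. Escalation rests on unblinded sponsor review with PK modelling during the study (Protocol 6.4.3) and on projection from observed data (Protocol 6.6.1). The exposure limits are set on Cmax and AUC24 (Protocol 4.3.3), not on AUClast.

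A reader might also infer a loss of about 1.8-fold from ignoring pairing. That figure assumes an unpaired regression with a wrong variance, which nobody plans. Most participants appear at most doses, so between-participant differences largely cancel in the geometric means, and the real loss is about 1.2-fold.

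The remedy has a limit of its own. Doses ascend by period in Cohort 1, so the slope absorbs any period trend unless Cohort 2 or repeated dose levels break the link. The box plots share this weakness, but a narrow interval could hide it.

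**Conclusion.** The point holds as a low-severity improvement. The plan assigns the dose-exposure question to unlinked by-dose plots without an estimate or interval, although the crossover was justified partly by within-participant PK assessment. A power model is feasible at this size: slope SE about 0.035 and 90% half-width about 0.06 under the assumed 40%/25% CVs, 32 profiles and half-log steps. The gain over an unpaired slope is about 1.2-fold (1.08 to 1.34 for within-CV 40% to 20%). The main benefit is having a reportable estimate at all.

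It would go too far to say that the plots are distorted. Truncation may affect AUClast(dn), one of three parameters. Its size depends on half-life and assay limit, which the public text does not show. The benefit is for later dose planning, not for escalation within this study.

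**What to change.** Keep the box plots and join each participant's points across doses. Add to SAP 6.3.1:

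- A power model of ln(Cmax), ln(AUCinf) if data permit, and ln of a common-interval AUC on ln(dose), with participant as a random effect, using fasted non-Japanese data. AUC0–24 is a natural choice of interval because the exposure limits use it. It is not among the derived parameters in Protocol Table 4 or SAP Tables 2 and 3, so it must be added. If the lowest dose is not quantifiable to 24 h, use a shorter common interval.
- The slope with its 90% CI, labelled as estimation and not as a test.
- A sentence beside the slope that dose and period rise together in Cohort 1, so a period trend cannot be excluded.
- A note that AUClast(dn) is read as supportive, alongside the counts above the assay limit.

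The cost is a few lines based on the mixed-model code already in SAP Appendix 1, one derived parameter and one more exploratory table. No new samples or visits are needed.
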